COMIRB Protocol

COLORADO MULTIPLE INSTITUTIONAL REVIEW BOARD [name] [contact] [contact]

- 1
- 2 Protocol #: 17-0611
- 3 Project Title: Comparison of braces for treatment of Sever's disease
- 4 Principal Investigator: [name]
- 5 **Version Date:** 03/25/2020
- 6

7 I. Hypotheses and Specific Aims:

8 Primary Aim: To compare two types of braces: The X Brace (The X Brace, Grand Rapids, MI) and 9 Cheetah Heel Cups (Tuli's[®], Medi-Dyne, Colleyville, TX), in pain reduction for barefoot athletes (e.g. 10 karate, gymnasts, dancers) diagnosed with Sever's disease (calcaneal apophysitis)

- 12 Hypothesis 1 - The Cheetah Heel Cup will be significantly more effective than The X Brace 13 in reducing pain for barefoot athletes diagnosed with Sever's disease, demonstrated by a 14 mean score difference greater than the minimal detectable difference (7 points) on the 15 OxAFQ-C in the physical domain.
- 16

11

17 II. Background and Significance:

18 Sever's disease is an osteochondrosis of the calcaneal apophysis due to frequent repetitive foot 19 impact and repeated traction from the Achilles tendon, which attaches to the apophysis.¹ Though 20 there remains uncertainty about the exact pathomechanics of this ailment, it is generally 21 considered an overuse injury affecting active skeletally-immature children aged 8-14 years.² Identified risk factors include high levels of athletic activity,³ increased BMI,^{4,5} and anthropometric 22 23 differences compared to a normative peer group including increased weight, height, ankle range of 24 motion, waist circumference, and foot posture index.⁵ A recent, large cross-sectional study 25 examining visits to primary care practices reported an incidence of 3.7 per 1,000 patients ages 6-17 26 with a median age of 10 years for girls and 12 years for boys.⁶ One systematic review reports that 27 Sever's accounts for 2%-16% of musculoskeletal complaints in children.⁷ This condition, which 28 presents as heel pain with physical activity, is one of the most common pathological entities among 29 this age group and a serious concern for growing athletes.⁶

30

Sever's disease has real and tangible effects on quality of life.² Children with this condition report 31 32 greater pain and discomfort, dissatisfaction with their symptoms, and less happiness than 33 asymptomatic peers.² It is also suggested that children may postpone treatment as they have the 34 "ability and the competitive motivation to endure the pain... for an extended period of time," 35 which can delay healing and prolong pain. Even despite that the pain associated with Sever's is 36 often so severe that the child will limp to relieve pressure on the affected heel during or after 37 physical activity.^{3,8,9} 38

- 39 It is widely accepted and scientifically confirmed that physical activity improves child health with
- 40 positive effects on adiposity, musculoskeletal health and fitness, and cardiovascular health.¹⁰
- 41 Beyond the health benefits of physical activity alone, participation in sports at this crucial age
- enhances psychological and social health outcomes.¹¹ Athletes with Sever's symptoms are limited 42

43 in their ability to participate in physical activity and athletics, and it is suggested that active

44 intervention in the management of Sever's is most appropriate to improve quality of life and

outcomes without substantial time lost from sport or physical activity.² Therefore, efficient and 45

- effective treatment is essential, especially for active and competitive athletes. 46

47 48 Standard treatment for Sever's disease is placement of heel cups in shoes and stretching or 49 physical therapy. These interventions are effective in reducing Sever's patients' heel pain.¹²⁻¹⁶ A 50 retrospective study showed that with treatment with a heel cup or other foot orthoses, symptoms improved within 2 months.⁸ However, there remains a distinct lack of randomized control trials 51 evaluating treatments for Sever's in the literature.¹⁷ For the many young athletes with Sever's who 52 53 participate in barefoot sports such as gymnastics, dance, or tae kwan do, the standard treatment is 54 inadequate. They cannot use the recommended heel cups, which are placed in an athletic shoe. 55 Currently, two braces are commonly used for barefoot athletes with Sever's: Cheetah Heel Cups 56 and The X Brace. Neither of these braces are currently FDA approved as they are not considered 57 medical devices and are marketed as an insert. Health care providers often recommend barefoot 58 athletes purchase these braces, but no published studies evaluating their effectiveness exist in the 59 established literature. This study will compare these two braces in an investigator-blinded, 60 randomized control trial in order to contribute to the understanding of standard treatment for 61 barefoot athletes with Sever's disease and improve patient outcomes by affecting clinical practice. 62 In light of the paucity of information on and the importance of optimizing patient outcomes to 63 improve quality of life and maintain an active lifestyle for young barefoot athletes, this prospective, 64 randomized treatment study will compare the effectiveness of two braces in decreasing pain 65 severity in barefoot athletes diagnosed with Sever's disease. 66 67 III. Preliminary Studies/Progress Report: 68 No preliminary studies have been conducted at this institution. 69 70 IV. Research Methods 71 A. Outcome Measures: 72 i. Primary Outcome: Oxford Ankle Foot Questionnaire for Children (OxAFQ-C) Scores 73 ii. Visual Analog Scale (VAS) Pain Score 74 iii. Subject-Reported Compliance with Brace Use 75 1. Hours per week the brace was worn with barefoot sport activity 76 iv. **Rest from Sport** 77 1. Amount of time per week taken off from barefoot sport due to pain (if 78 applicable) 79 Acceptability of Brace ν. 80 1. Comfort (Comfortable: Y/N) 81 2. Appearance (Acceptability: Y/N) 82 3. Perceived Effect on Athletic Performance (Improvement: Y/N) 83 Pain Medicine Usage vi. 84 1. Weekly dosage of pain medicine (if applicable) 85 B. Explanatory Variables: 86 i. Demographic 87 1. Name and Medical Record Number 88 2. Date of Birth 89 3. Age at time of visit

90		4. Gender
91		5. Ethnicity
92		6. Weight
93		7. Height
94		8. BMI
95		9. Athletic participation
96		10. Primary sport
97		11. Hours per week in a barefoot sport
98		ii. History
99		1. Previous diagnosis of Sever's or calcaneal apophysitis
100		a. Brace previously used
101		
102		
103		4
104		
105		
106		
107		
108		
109		
110		
111		
112		
113		
114		
115		Figure 1. Cheetah Brace Figure 2. The X Brace
116		
117	C.	Description of Population to be Enrolled:
118		Barefoot athletes who present to sports medicine clinic for foot, ankle, or heel pain.
119		i. Inclusion Criteria:
120		1. Aged 7-14 years
121		2. Participate in barefoot sports including: martial arts, dance, gymnastics, or
122		acrobatics
123		3. A clinical diagnosis of Sever's or calcaneal apophysitis
124		ii. Exclusion Criteria:
125		1. History of foot/ankle surgery
126		2. History of rheumatologic diagnoses
127		3. Prisoners, pregnant females, individuals with limited decision-making capacity
128		
129	D.	Study Design and Research Methods
130		i. Human Subject Considerations
131		1. All patients will have an established relationship with a Children's Hospital
132		Sports Medicine Physician.
133		2. All PHI will be stored within REDCap.
134		ii. Study Design: Randomized Treatment Study
135		iii. Methods:

136	1. Subjects will be recruited face-to-face by a study team member at time of initial
137	visit, diagnostic clinical visit, or phone call initiated by [name]. Subjects
138	recruited via phone call will be patients of study personnel. Patients and
139	families interested in participating in the study will be contacted by a member
140	of the study team to set up a research only consent visit. If they cannot come
141	into clinic, the informed consent and assent will be sent to the family and a
142	research assistant with call the family, either via phone or video call, to go over
143	the consent and assent in real time and to answer any questions. After a signed
144	consent or assent form is received by the research assistant, the assigned brace
145	will be sent in the mail to the family and the associated questionnaires will be
146	sent via email.
147	2. Subject will be screened for inclusion/exclusion (enrollment) criteria by study
148	team member through chart review.
149	3. If subject meets enrollment criteria, they and a legal guardian will be consented
150	face-to-face by a study team member.
151	a. Consent will be sought from subjects ages 13-14.
152	b. Assent will be sought from athletes younger than 13 years of age.
153	c. Consent will be sought from parents of subjects ages 7-14.
154	4. [name] or designated staff will answer any questions after the patient and
155	his or her parents have read and reviewed the informed consent and assent
156	forms. It will be emphasized to the patients that their decision to participate in
157	the study will in no way impact their treatment. Comprehension will be
158	assessed by reviewing the consent forms with the patient and his or her parents
159	thoroughly and asking the subjects questions requiring more than a simple
160	yes/no answer.
161	a. Patients and parents will sign the appropriate line on the informed
162	consent/assent form.
163	b. Consent procedures will take place in a private room or over a private
164	call.
165	5. Subject will complete initial demographics survey, OxAFQ-C, and VAS.
166	6. Subject will be randomized into either the Cheetah Heel Cup or The X Brace
167	treatment group. The randomization scheme will be independently created by
168	the research assistant. The random assignment will be kept blind to the PI and
169	statistician.
170	7. Subject will receive their assigned brace in the mail following their consent visit.
171	Subjects will receive an activity and rest log in the mail with their
172	brace. This is a weekly log and will help subjects track their weekly
173	activity in their barefoot sport (in hours), amount of time spent in
174	brace during barefoot sport (in hours), and any rest time taken from
175	their barefoot sport (in hours). This log is optional, but encouraged,
176	to fill out as it will not be submitted to the researchers. The
177	intended purpose of the log is to aid in answering the monthly
178	questionnaire on weekly activity, time in brace, and rest time.
179	8. At 1, 2, and 3 months, a study team member will email the subject's parent the
180	OxAFQ-C, VAS and questionnaire on activity/brace usage. During this time,
181	subjects will also answer questions pertaining to pain medicine use and any
182	adverse outcomes from brace use. A reminder phone call will be made if the

183 184 185 186 187		iv.	questionnaires have not been completed within 5 days. Subjects will not be seen after the visit where consent was obtained, unless an adverse outcome arises requiring an assessment by [name].Planned Duration of Study1. Two-years from COMIRB approval date to allow for adequate enrollment
188		۷.	Duration of Participation of Each Subject
189			1. About 30 active minutes for consent and surveys
190			2. About 3 months for course of clinical care and resolution of symptoms
191		vi.	Patient Incentives
192			1. Participants will receive a free brace after enrolling into the study. Upon
193			successful completion of the study (once month 3 survey is
194			completed), subjects will receive a \$30 gift card in the mail.
195	_		
196	Ε.	Descrip	otion, Risks and Justification of Procedures and Data Collection Tools:
197		١.	Potential Risks to Subjects:
198			I nere are no anticipated risks in this study beyond those of standard care and daily
199			living. There are no documented adverse outcomes associated with either brace
200			that is known to the study team. Any adverse outcomes (skin irritation/rash) that
201			anses during the study period will be documented during the monthly austion paires sont out to subjects. Additionally an unlikely and uncommon risk of
202			this study is that PHI may be unintentionally disclosed to an outside party. We will
203			nut forth our best effort to keep the information about subjects secure, and we
204			believe that the risk of accidental disclosure is minute. Identifying data will be
206			protected as per REDCap protocol after subjects have been assigned a study
200			number
208			
209		ii.	Plan to Protect Subjects/Mitigate Risks:
210			Subjects will be instructed to call the research assistant if any adverse outcomes
211			arise (skin irritiation/rash that causes discomfort or concern). The research
212			assistant will document the adverse outcome in REDCap, and relay the message
213			onto [name] who will contact the family to discuss the adverse event and if
214			any of the following is needed: a new brace size, discontinued use of the
215			brace/removal from study, a research visit to assess the adverse reaction. A
216			REDCap database will be utilized for the organization and storage of patient
217			information when necessary. Patients will be identified using individualized study
218			numbers that will be stored securely in the REDCap database. Data containing
219			spreadsheets will refer to patients only by the individualized study numbers,
220			excluding all PHI.
221			
222		iii.	Participant Discontinuation Criteria:
223			1. Subject participation will be discontinued if:
224			a. Subject no longer wishes to participate in the study
225			b. Subject sustains an additional musculoskeletal injury or serious illness
226			(hospitalization, injury to lower body requiring a visit to
227			doctor).
220			c. subject fails to follow-up with clinical care.

229		d. Adverse reaction causing [name] to determine a discontinuation of
230		the brace.
231		
232	iv.	Data Collection Tools:
233		1. Demographic and clinical data will be collected from the subjects' charts from
234		EPIC and through subject input to REDCap questionnaires. REDCap will be used
235		to store all study data electronically. REDCap is a secure, web application
236		designed to support data capture for research studies. REDCap is hosted by the
237		University of Colorado-Denver Development and Informatics Service Center
238		(DISC).
239		2. The Oxford Ankle Foot Questionnaire for Children (OxAFQ-C) is used to measure
240		subjective well-being for child patients (aged 5-16) affected by foot and ankle
241		conditions using issues that are considered important to children. Typical
242		clinical assessments fail to capture the child patient's perspective and may not
243		accurately reflect how children function in their usual environments. The
244		OxAFQ-C was therefore designed to supplement clinical assessments to
245		evaluate the effectiveness of interventions for ankle/foot problems in children.
246		It is a short (15-item) questionnaire and reported as valid and reliable in
247		English ¹⁸ and Spanish and as responsive and longitudinally valid ¹⁹ . There are
248		three domains to the OxAFQ-C: physical, school and play, and emotional well-
249		being. Scores on the OxAFQ-C range from 0 to 100 with higher scores
250		indicating better functioning and higher well-being.
251		
252	۷.	Data Management:
253		1. Patients will be assigned patient study identifiers. These identifiers will be used
204		for the identification of all study materials, and will only be linked to the
200		patient's name, medical record number, or other PHI through REDCap. Non-
200		information will be stored with Dedeen. Dedeen is a secure web application
201		designed to support data capture for research studies, providing user friendly
250		web based case report forms, real time data entry validation (e.g. for data
209		types and range checks) audit trails and a de identified data event mechanism
200		to common statistical packages (SDSS_SAS_Stata_P/S_Dlus). The system was
201		developed by a multi institutional consortium which includes University of
202		Colorado Denver and was initiated at Vanderbilt University. The database is
264		hosted at the University of Colorado-Denver Development and Informatics
265		Service Center (DISC) which will be used as a central location for data
266		processing and management REDCan data collection projects rely on a
267		thorough study-specific data dictionary defined in an iterative self-documenting
268		process by all members of the research team with planning assistance from the
269		DISC. The iterative development and testing process results in a well-planned
270		data collection strategy for individual studies. Both REDCan and REDCan Survey
271		systems provide secure web-based applications that are flexible enough to be
272		used for a variety of types of research provide an intuitive interface for users to
273		enter data and have real time validation rules (with automated data type and
274		range checks) at the time of entry. These systems offer easy data manipulation
275		with audit trails and reporting for reporting monitoring and querving patient

276 277 records, and an automated export mechanism to common statistical packages (SPSS, SAS, Stata, R/S-Plus).

278 279 280

281 282

vi. **Potential Scientific Problems:**

The investigators recognize no other potential scientific problems at this time.

F. Data Analysis Plan:

- 283 i. Sample Size: We will use a linear mixed model to test the null hypothesis that the 284 difference in OxAFQ-C physical domain scores between the The X Brace and 285 Cheetah Heel Cups does not depend on time (group*time interaction). Means for 286 treatment group at each time point were estimated based on a related RCT by James et al. ¹³. The common standard deviation for all OxAFQ-C physical domain 287 scores was assumed to be 6 and the correlation between time consecutive points 288 289 was conservatively assumed to be 0.6 based on this previous RCT. We intend to 290 use a one-to-one block randomization scheme to ensure equal allocation of 291 patients to each treatment group. Assuming a Type 1 error rate of 0.05, a sample 292 size of 44 participants total, 22 in each group, will provide 0.9 power to reject the 293 null hypothesis of no group*time interaction based on the Hotelling-Lawley test 294 statistic with an alpha level of 0.05. Assuming there is no missing data, no time 295 varying covariates, and the repeated measures are consistently collected (general 296 linear mixed model reversibility criteria is met), the Hotelling-Lawley trace statistic 297 is equivalent to the statistical test, the Wald statistic with Kenward-Roger degrees of freedom, described in the data analysis plan.²⁰. With an expected 30% loss to 298 299 follow up, we will inflate the sample size to account for attrition, for a total 300 enrollment goal of 58. The clinic treats 10 barefoot athletes with a clinical 301 diagnosis of Sever's Disease who meet the eligibility criteria for this study each 302 month. We expect a consent rate of approximately 50%. At an effective enrollment 303 rate of 5 patients per month, we will reach the enrollment goal of 58 participants 304 within 12 months. All samples size calculations were performed with GLIMMPSE, 305 an internet based open source software program capable of computing power and 306 sample size for multi-level and longitudinal research designs²¹
- 307 308
- 309

310 311 Table 1. Expected OxAFQ-C physical domain scores based on data from James et al^{13}

Treatment	1 month	2 months	3 months
Cheetah Heel Cups	67 (±6)	83 (±6)	85 (±6)
The X Brace	64 (±6)	82 (±6)	78 (±6)

312 313

314

315

316

317

318

iii. Analysis Plan: Demographic and clinical characteristics will be summarized and compared between the two treatment groups using chi-squared and two-sample ttests for categorical and continuous data, respectively. Imbalance between groups will be adjusted for in subsequent statistical analyses. For hypothesis 1, Linear mixed model regression analyses will be used to compare group differences

ii.

319 (Cheetah Brace vs X brace) across the 1, 2 and 3 month visits. We will test the null 320 hypothesis that the difference between groups does not depend on time 321 (group*time interaction). The parameter estimate will be tested using the Wald 322 statistic with Kenward-Roger degrees of freedom and an alpha level of 0.05. 323 Intent-to-treat analyses will be performed for all the primary outcome variables. A 324 per-protocol analysis will also be performed. For the secondary analysis, the other 325 two domains of the OxAFQ-C questionnaire as well as VAS pain scores will be 326 analyzed using separate linear mixed models that iwill also test the group*time 327 interaction. Linear regression models will also be used to compare overall 328 compliance. Logistic regression models will be used to test the null hypothesis of 329 no difference between groups for each of the three brace acceptability metrics 330 (comfort, appearance, and perceived effect on athletic performance).

331

334

335

336

337

338

339

340

341 342

343

344

345

350

332 333

G. Summarize Knowledge to be Gained:

It is common practice to provide heel cups and stretching exercises for patients with Sever's. Because these heel cups cannot be used in barefoot athletes, alternative braces are used. Currently, there are two commonly used braces in barefoot athletes, Cheetah Heel Cups and the The X Brace. No previous study has looked at the effectiveness of these braces. This study would compare these braces in a blinded clinical trial to determine if these braces are effective and if one brace is more effective in decreasing severity of pain in barefoot athletes with Sever's. This study will contribute to the understanding of treatment for barefoot athletes with Sever's disease and will improve patient outcomes by affecting clinical practice. In order to improve quality of life and allow young athletes to remain active, this prospective, randomized treatment study will compare the effectiveness of two braces in decreasing pain severity in barefoot athletes diagnosed with Sever's disease.

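### Hypothesis 1 sets a bar of more than 7 points at no named visit, but Table 1 expects differences of 3, 1 and 7, so the stated 0.9 power does not apply to that bar

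*Combined protocol and SAP*

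**What the plan says.** Section I, Hypothesis 1, is the protocol's only hypothesis. It states that "The Cheetah Heel Cup will be significantly more effective than The X Brace" in reducing pain, and that this will be shown by a "mean score difference greater than the minimal detectable difference (7 points) on the" OxAFQ-C physical domain. It does not say at which visit, or whether an average over visits is meant.

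Section IV.F.i (Sample Size) gives the planning values. Table 1 is titled "Expected OxAFQ-C physical domain scores based on data from" a related randomised trial, and prints these means:

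| | Month 1 | Month 2 | Month 3 |
|---|---|---|---|
| Cheetah | 67 | 83 | 85 |
| X Brace | 64 | 82 | 78 |

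The common SD for the physical domain "scores was assumed to be 6 and the correlation between time consecutive points" "was conservatively assumed to be 0.6 based on this previous RCT". On this basis a sample "size of 44 participants total, 22 in each group, will provide 0.9 power to reject the" null hypothesis of no group-by-time interaction, using the Hotelling-Lawley statistic.

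Section IV.F.iii (Analysis Plan) assigns the same interaction test to Hypothesis 1: a mixed model over months 1, 2 and 3, with a Wald statistic, Kenward-Roger degrees of freedom and alpha 0.05. It does not mention 7 points.

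**The concern.** The hypothesis, the sample size and the analysis use two standards that are not connected. The hypothesis asks for a difference above 7 points. The sample size and the analysis ask whether the difference between braces changes over time. Someone reading Section I together with the power statement would naturally attach 90% to the 7-point claim.

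Two things are at stake. First, if the 7-point wording is used to judge the trial, a real advantage of the size the sponsor planned for would often fall short of it. Second, the same data could be reported either way. Suppose the interaction is significant and the month-3 difference is 6 points: the plan does not say whether Hypothesis 1 has been supported. With no visit named, the bar could also be compared with whichever visit shows the largest difference.

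**Working it through.** **Inputs** (all from Section IV.F.i). Expected differences, Cheetah minus X Brace: 67 − 64 = 3, 83 − 82 = 1 and 85 − 78 = 7, with mean 11/3 = 3.67. SD 6, correlation of consecutive visits 0.6, 22 per arm, alpha 0.05. The correlation between months 1 and 3 is not given, so two patterns are used: 0.6 throughout (compound symmetry), or 0.36 for that pair (first-order autoregressive).

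**1. The plan's own power figure.** For the 2-df interaction, let θ hold the successive differences of (3, 1, 7): θ = (3 − 1, 1 − 7) = (2, −6). The noncentrality is λ = (n/2) θ′(CΣC′)⁻¹θ, where C is the matrix of successive differences and Σ the covariance of the three visits.

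- Compound symmetry: CΣC′ = 36 × 0.4 × [[2, −1], [−1, 2]], so θ′(CΣC′)⁻¹θ = (8 − 24 + 72)/43.2 = 1.296 and λ = 11 × 1.296 = 14.26. Noncentral F on (2, 41) df gives power 0.913.
- Autoregressive: λ = 14.00, power 0.908.

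Under both patterns, 22 is the smallest number per arm that reaches 0.90. The stated 0.9 is reproduced, so the inputs are being read as the sponsor meant them.

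**2. Chance that the observed difference exceeds 7.** SE at one visit = 6 × √(2/22) = 1.81. P = 1 − Φ((7 − d)/1.81).

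| Comparison | Expected d | SE | P(observed > 7) |
|---|---|---|---|
| Month 1 | 3 | 1.81 | 1.4% |
| Month 2 | 1 | 1.81 | 0.05% |
| Month 3 | 7 | 1.81 | 50% |
| Three-visit average | 3.67 | 1.49–1.55 | 1.3–1.6% |

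The SE of the average is √(36 × s/9 × 2/22), where s is the sum of the nine correlations: 6.6 for compound symmetry (SE 1.55) and 6.12 for the autoregressive pattern (SE 1.49).

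The month-3 figure does not depend on SD, correlation or sample size, because the estimate is distributed symmetrically around the bar. More patients would not change it. At 22 per arm, a 90% chance of observing more than 7 at one visit would need a true difference of 7 + 1.2816 × 1.81 = 9.3 points.

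**3. Both standards together.** In 200,000 simulated trials per correlation pattern, a significant interaction together with a month-3 difference above 7 occurred in 48.0–48.4%.

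**4. A plain month-3 comparison.** Under the same inputs, the power of a two-sided 5% test is about Φ(7/1.81 − 1.96) = Φ(1.91) = 0.97. If 30% of the 58 enrolled are lost, 58 × 0.7 = 40.6 remain, about 20 per arm. Then SE = 6 × √(2/20) = 1.90 and power is about Φ(7/1.90 − 1.96) = 0.96.

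**The case against.** The strongest reply is that 7 points is not a decision rule at all. The analysis plan gives Hypothesis 1 a specified test, the interaction, and that test has the power claimed for it. This stands. A reader might infer that the trial would miss its success criterion at least half the time. The documents do not support that: nowhere do they say that a significant result with a smaller difference would be declared a failure. The 48% belongs to a combined rule that the plan does not state.

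Three further points also stand.

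- If a difference above 7 at any visit counted, with no significance requirement, the chance of meeting the bar could not be below the month-3 value of 50%. Simulation gives 49.9–50.3%. On that reading, about half is right and at least half is not.
- Table 1 prints whole numbers. If each mean was rounded to the nearest point (an assumption), the planned month-3 difference could lie between 6 and 8, and the chance of exceeding 7 between about 29% and 71%.
- A reader might argue that a minimal detectable difference is by nature a threshold for one child's score and so cannot serve for group means. The documents do not define the term or say how 7 was derived, so no weight is put on this.

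It is also fair to say that asking for a difference of stated size is a legitimate choice, and that an effect planned exactly at such a size always gives about an even chance that the estimate exceeds it. That explains the 50%. It does not connect the 7-point bar to the stated power or to the analysis.

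**Conclusion.** The point holds as a mismatch between the only hypothesis and the rest of the plan. The wording of Hypothesis 1 sets a bar that the sample size does not power and the analysis does not test. Taking Table 1 as printed, the chance of observing more than 7 points is about 50% at month 3, under 2% at the other visits or on average, and about 48% with a significant interaction as well as month 3 above 7. If Hypothesis 1 is read as a statement about true means, Table 1 itself does not satisfy it, since 7 is not greater than 7.

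A reader might infer that the trial is underpowered or that its power calculation is wrong. Neither follows: 0.9 is correct for the interaction, and a month-3 comparison would have more. These figures rest on SD 6, 22 per arm with complete data, normally distributed estimates, and one of the two correlation patterns above. The 50% rests only on a planned month-3 difference of exactly 7. This should be fixed; it does not invalidate the design.

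**What to change.** - **Hypothesis 1 (Section I):** name month 3, where Table 1 places the largest expected difference. Define success as a statistically significant month-3 difference in OxAFQ-C physical domain score favouring Cheetah, reported with its 95% CI. Keep 7 points only as a benchmark for interpreting that estimate and interval.
- **Analysis Plan (Section IV.F.iii):** name the month-3 group contrast from the mixed model already planned as the test of Hypothesis 1. Rewording Section I alone would leave this section testing something else.
- **Sample Size (Section IV.F.i):** state the power of that contrast, about 0.97 with 22 per arm under Table 1.
- **If the sponsor keeps a difference above 7 as the criterion:** state that the chance of meeting it at month 3 under Table 1 is about 50%, not 90%.

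The cost is a short revision of the hypothesis, the primary contrast and the sample-size text. The month-3 questionnaire is already scheduled, so no new data or patients are needed. The drawback is a weaker claim: Cheetah is better, instead of better by more than 7 points.

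### Comfort and appearance of the brace are recorded only as Yes/No, which gives up power that a graded item would keep at almost no cost

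*Combined protocol and SAP*

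**What the plan says.** Section IV.A.v (Outcome Measures, Acceptability of Brace) lists three items, all answered Yes or No: "Comfort (Comfortable: Y/N", "Appearance (Acceptability: Y/N" and "Perceived Effect on Athletic Performance (Improvement: Y/N". No graded form of any of them is listed.

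Section IV.F.iii (Analysis Plan) tests them formally: "Logistic regression models will be used to test the null hypothesis of" and, continuing, "no difference between groups for each of the three brace acceptability metrics". It names no time point, expected Yes rate, effect size or power for these tests.

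The sample size in section IV.F.i is for the OxAFQ-C physical domain only: "size of 44 participants total, 22 in each group, will provide 0.9 power" for the group-by-time interaction.

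A graded scale is used elsewhere in the same questionnaires, but for a different construct. Section IV.A.ii lists the "Visual Analog Scale (VAS) Pain Score". Section IV.D.iii has the child complete it at entry ("Subject will complete initial demographics survey, OxAFQ-C, and VAS"), and it is emailed to the parent at months 1, 2 and 3.

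**The concern.** Comfort, and how a child feels about a brace's appearance, can reasonably be seen as matters of degree. The plan reduces each to two categories when the answer is collected and then tests the result for a difference between braces. Cutting a graded response in two discards information, and the cost is greatest in small samples and when most answers fall on one side.

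If the braces relieve pain about equally, acceptability could well guide the choice between them. A comparison with little power may then be read as showing no difference in comfort when a moderate or large one exists. Nothing in the documents requires a binary answer.

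This point covers comfort and appearance. The performance item shares the Yes/No format but is left aside here.

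**Working it through.** **1. The plan's own figure.** Table 1 gives differences between braces of 3, 1 and 7 points at months 1, 2 and 3. The two interaction contrasts are 3 − 1 = 2 and 3 − 7 = −4. With SD 6, correlation 0.6 (compound symmetry) and 44 children, the contrast covariance is 36 × [[0.8, 0.4], [0.4, 0.8]] and the noncentrality is (44/4) × 1.296 = 14.26. The noncentral F with 2 and 41 df gives power 0.913. An AR(1) correlation gives 0.908. The stated 0.9 is reproduced, and it concerns this outcome only.

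**2. Children available.** 22 per arm as planned. If 58 enrol and 30% are lost, 58 × 0.7 = 40.6 remain, or about 20 per arm.

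**3. Assumptions, since the plan gives none for acceptability.** An underlying normal rating shifted by d SD between braces; Yes in a share p₁ = 50% to 80% of the worse arm; two-sided α = 0.05. The better arm's Yes rate is then p₂ = Φ(Φ⁻¹(p₁) + d).

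**4. Tests compared, 22 per arm.**
- Yes/No: likelihood-ratio test from logistic regression, by exact enumeration of two binomials. Its type I error at d = 0 is 0.050-0.058.
- Continuous rating: t-test with 42 df and noncentrality d√(22/2). For d = 0.8 this is 0.8 × 3.317 = 2.65.

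| True difference | Yes/No power | Continuous power | Loss (points) |
|---|---|---|---|
| 0.3 SD | 0.11-0.13 | 0.16 | 3-5 |
| 0.5 SD | 0.20-0.26 | 0.37 | 11-16 |
| 0.8 SD | 0.39-0.54 | 0.74 | 19-35 |
| 1.0 SD | 0.51-0.72 | 0.90 | 18-39 |

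At 20 per arm the loss is 11-14 points at 0.5 SD and 20-33 points at 0.8 SD.

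**5. A coarser graded item.** A 5-level cut of the same rating, compared by a Mann-Whitney test (simulation, 4,000 runs, d = 0.8, 22 per arm):

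| Yes, worse v better arm | Yes/No | 5-level | Gain (points) |
|---|---|---|---|
| 50% v 79% | 0.543 | 0.665 | 12 |
| 70% v 91% | 0.435 | 0.605 | 17 |
| 80% v 95% | 0.386 | 0.537 | 15 |

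These gains depend somewhat on where the categories fall.

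**6. Choice of logistic test.** The plan does not say which test accompanies the logistic model. The Wald test does worse in the same three rows (0.487, 0.249 and 0.062), so the likelihood-ratio figures are the kinder ones for the plan.

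**7. Adoption part-way through.** If only 11 children per arm give a graded answer, the t-test has power 0.43 at 0.8 SD and 0.20 at 0.5 SD. The Yes/No test in all 22 has 0.39-0.54 and 0.20-0.26, so the gain is about nil or negative. With the formula in step 4 (noncentrality d√(n/2), 2n − 2 df), 14 per arm gives 0.53 and 0.25, and 15 per arm gives 0.56 and 0.26. Under these assumptions about 15 of 22 graded answers (68%) are needed to match the Yes/No test across the whole range.

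**The case against.** The strongest reply is that the size of the loss is the reviewer's, not the trial's. With no Yes rates or effect sizes in the plan, a reader might take 11 to 35 points as an established property of this design. It is not: it belongs to the 0.5 to 0.8 SD rows. This stands, and the range has to be labelled as assumed.

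A reader might also infer that the children already complete the scale that is needed. They do not. The existing VAS measures pain, and at follow-up it goes to the parent's email. It shows only that the response format is in use, not that a comfort or appearance rating would be close to normal at ages 7 to 14. A ceiling is most plausible where the computed gain is largest (80% v 95% Yes). It shrinks the gain without removing it. With the rating capped so that 26% of the worse arm and 56% of the better arm sit at the maximum, a rank test still has simulated power of about 0.66-0.68, against 0.39 for Yes/No.

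A third tempting reading is that a report of no difference is the likely outcome whenever one brace is clearly less comfortable. At 1.0 SD the Yes/No test succeeds more often than not throughout (0.51-0.72), and at 0.8 SD with 50% v 79% Yes it has 0.54.

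Finally, whether a child accepts the look of a brace is a legitimate yes-or-no question, and citing no guideline for it is not an error. That is a good reason to keep the Yes/No item, but not a reason to collect nothing else.

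**Conclusion.** The point holds as an optional design improvement. Comfort and appearance are collected only as Yes/No and tested between arms of about 20 to 22. In every case examined a graded item analysed in full had more power when all completers answered it. Under a latent normal rating with 50-80% Yes in the worse arm, the shortfall against a continuous rating is about 11 to 35 points for differences of 0.5 to 0.8 SD and 3 to 5 points at 0.3 SD. Against a 5-level item it is about 12 to 17 points at 0.8 SD.

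A reader should not infer that the trial's main result is weakened. Acceptability is non-primary, Hypothesis 1 does not mention it, and the plan claims no power for it. The documents do not say how far enrolment has gone, so the gain still obtainable is uncertain.

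**What to change.** - **Section IV.A.v:** add one graded comfort item and one graded appearance item beside the existing Yes/No questions, either a 0-100 VAS or a 5-level ordered response.
- **Section IV.F.iii:** compare the braces on the graded scale, by a linear model or rank test for a VAS, or a proportional-odds model or rank test for a 5-level item. Report the Yes/No percentages descriptively.
- **If enrolment has already begun:** collect the graded items from then on, and keep the Yes/No logistic comparison in all children as the planned test unless most completers will have a graded answer. Make that choice from the count of graded answers expected, without looking at results by arm.

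The cost is two REDCap items, a sentence or two in the analysis plan and a few seconds more per questionnaire. Children who have already finished will have no graded rating. No extra patients, visits or staff are needed.
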